**Figure 4-1 Trial Design for Subjects Assigned to the MC2-01 Cream**

\*Follow-up visits will be required only for subjects who have unresolved AEs or whose calcium levels have not returned to pre-treatment levels at the End of Treatment visit.

**Figure 4-2 Trial Design for Subjects Assigned to the Active Comparator**

\*Follow-up visits will be required only for subjects who have unresolved AEs at the End of Treatment visit.

## 4.2 Trial Endpoints

### Primary Endpoints

#### For all subjects:

Pharmacokinetic (PK) parameters ( $AUC_{0-t}$ ,  $AUC_{0-\infty}$ ,  $AUC_{0-7}$ ,  $C_{max}$ ,  $T_{max}$ , and  $T_{1/2}$ ) of active ingredients and their main metabolites at Week 4. For a given analyte, the PK parameters  $AUC_{0-t}$ ,  $AUC_{0-\infty}$ ,  $T_{max}$ , and  $T_{1/2}$  will be calculated if data allow. The PK parameters  $AUC_{0-7}$  and  $C_{max}$  will be calculated for all subjects;  $AUC_{0-7}$  will be an upper limit in case at least one time point shows a non-quantifiable level of the analyte, and  $C_{max}$  will be an upper limit in case all

time points show non-quantifiable levels of the analyte.  $T_{max}$  will be calculated in case at least one time point shows quantifiable levels of the analyte.

#### For subjects assigned to the MC2-01 cream:

PK parameters ( $AUC_{0-t}$ ,  $AUC_{0-\infty}$ ,  $AUC_{0-7}$ ,  $C_{max}$ ,  $T_{max}$ , and  $T_{1/2}$ ) of active ingredients and their main metabolites at Week 8. For a given analyte, PK parameters will be calculated under similar conditions as described for Week 4.

#### **Secondary Endpoints**

##### HPA axis evaluation for subjects assigned to the MC2-01 cream:

The number of subjects with a serum cortisol level of 18  $\mu\text{g}/\text{dL}$  or less at 30 minutes after ACTH challenge at Week 4 or Week 8.

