### 7.9.2 HPA axis suppression/ ACTH challenge test

For subjects assigned to the MC2-01 cream, adrenal function will be assessed in a challenge test with an intravenous dose of adrenocorticotropic hormone (ACTH) (cosyntropin). Measurement of serum cortisol levels pre- and post- stimulation with cosyntropin 0.25 mg is the accepted standard method used to evaluate adrenal suppression. The ACTH challenge test will be performed at Visit 1/Day 0, Week 4 and Week 8 visits. The test consists of blood sampling starting at 8 am ( $\pm$  30 minutes). Following the blood sample, an intravenous bolus injection of 0.25 mg cosyntropin is given at time zero (t=0 minutes). Serum cortisol concentration at t=30 minutes will reflect

stimulation of the adrenal glands induced by cosyntropin. The ACTH challenge test must be performed before application of the IP.

Since many people do not respond to the degree expected with cosyntropin stimulation, the following criteria have been established to denote a normal response:

1. pre-stimulation cortisol levels  $>5 \mu\text{g/dL}$  will be considered normal,
2. the 30-minute post-stimulation level should show an increment of  $\geq 7 \mu\text{g/dL}$  above the basal level, and
3. the 30-minute post-stimulation level should exceed  $18 \mu\text{g/dL}$ .

Therefore, a basal serum cortisol level  $\leq 5 \mu\text{g/dL}$ , or a 30-minute post-stimulation level  $\leq 18 \mu\text{g/dL}$ , or a post-stimulation increase (over basal)  $< 7 \mu\text{g/dL}$  constitutes the definition of HPA axis suppression in the trial.

Visit 1/Day 0: If HPA axis is suppressed at Visit 1/Day 0, the subject should be contacted because the application with the investigational product (IP) should be discontinued and an Early Termination visit should be performed (see [Section 7.16](#)).

Week 4: If HPA axis is suppressed at Week 4, the subject should be contacted and the application with the MC2-01 cream should be discontinued. The subject should continue in the trial and the ACTH challenge test is repeated at the Week 8 visit. If HPA axis suppression is noted at Week 8, the subject must return for a follow-up visit (see [Section 7.15](#)).

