### **8.3 Analysis Populations**

The analysis populations are defined as follows:

- **PK population:** all subjects in the Safety population who have received the planned application of treatment at the Week 4 or Week 8 visit, respectively, and have had at least one post-application blood draw for PK assessment at the corresponding visit.

- **Safety population:** all subjects who are randomized and have been dispensed the trial medication at Randomisation/Day 0, excluding subjects who return all of the trial medication unopened. The Safety population will be used for all safety analyses other than evaluation of the HPA-axis.
- **HPA population:** all subjects in the Safety population that are assigned to MC2-01 cream and who show normal HPA function at Baseline. Since the objective of the analysis is to estimate the risk to subjects with normal HPA function of HPA-axis suppression following treatment, subjects who meet the definition of HPA-axis suppression at Baseline will be excluded from the analysis. The HPA population will be used for the HPA axis suppression analysis.

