#### **8.8.1 HPA-axis suppression**

The number and proportion of subjects with HPA-axis suppression at Week 4 and Week 8 will be summarised.

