## 10.8.2 Analyses of Safety Endpoints

### 10.8.2.1 HPA-axis Suppression

The number and proportion of subjects with HPA-axis suppression at Week 4 will be summarised for the HPA population. Subjects with HPA-axis suppression at Week 4, was as described in the

protocol, contacted to discontinue use of MC2-01 cream. Subjects with HPA-axis suppression at Week 8 will be summarised overall and separately by HPA-axis suppression status at Week 4.

An additional analysis of the number and proportion of subjects with HPA-axis suppression will be summarised based on the test laboratory normal reference range established for the analytical method used by the test laboratory in the trial for the ACTH challenge test.

- In this analysis HPA suppression is defined as a 30-minute post-stimulation cortisol level  $< 14 \mu\text{g/dl}$  (test laboratory normal reference range of 14 to 36  $\mu\text{g/dl}$  for the 30-minute post-stimulation cortisol level). This analysis will be performed among MC2-01 cream subjects whose Baseline cortisol level is  $\geq 14 \mu\text{g/dl}$

All HPA-axis function test results (baseline, Week 4, Week 8, and Follow-up) will be presented in a by-subject listing for the Safety population.

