#### **10.8.2.2 Calcium Metabolism Endpoints**

All calcium metabolism data will be presented in a by-subject listing for the following parameters:

- Albumin-corrected serum calcium
- 24 hours urinary calcium excretion
- Ratio of urinary calcium to creatinine

Observed values and changes from baseline to Week 4 and Week 8 will be summarized using descriptive statistics for subjects in the Safety population assigned to MC2-01 cream.

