Generated on XXXXXX by XXXX / Uses: XXXX / Reference: Data Listing XXXX

Table 14.2.4.1 Summary of HPA-Axis Suppression (Based on Cosyntropin US Packing Insert)  
HPA Population

	MC2-01 Cream (N=XX)
HPA-Axis Suppression, n / N (%)	
Visit 3/ Week 4	XX/XX (XX.X)
Visit 5/ Week 8	XX/XX (XX.X)
HPA-Axis Suppressed at Week 4	XX/XX (XX.X)
HPA-Axis Not Suppressed at Week 4	XX/XX (XX.X)

Note: HPA-axis suppression is defined as a 30-minute post-stimulation cortisol level <18 µg/dL  
Generated on XX/XX/XX:XXXX by XXXXX / Uses: XXXX / Reference: Data Listings XXXX

*[Programming note: Denominator for Visit 5/Week 8 (Week 4 HPA-Axis Suppressed) row is subjects with HPA-Axis Suppressed at Week 8; denominator for Visit 5/Week 8 (Week 4 HPA-Axis Not Suppressed) row is subjects with HPA-Axis Suppressed at Week 8]*

Table 14.2.4.2 Summary of HPA-Axis Suppression (Based on Lab Reference Range)  
MC2-01 Cream Subjects with Baseline Cortisol Level  $\geq$  14  $\mu$ g/dl

MC2-01 Cream (N=XX)	
HPA-Axis Suppression, n / N (%)	
Visit 3/ Week 4	XX/XX (XX.X)
Visit 5/ Week 8	XX/XX (XX.X)
HPA-Axis Suppressed at Week 4	XX/XX (XX.X)
HPA-Axis Not Suppressed at Week 4	XX/XX (XX.X)

Note: HPA-axis suppression is defined as a 30-minute post-stimulation cortisol level  $<14 \mu$ g/dL  
Generated on XX/XX/XX:XXXX by XXXXX / Uses: XXXX / Reference: Data Listings XXXX

*[Programming note: Denominator for Visit 5/Week 8 (Week 4 HPA-Axis Suppressed) row is subjects with HPA-Axis Suppressed at Week 8; denominator for Visit 5/Week 8 (Week 4 HPA-Axis Not Suppressed) row is subjects with HPA-Axis Suppressed at Week 8]*

MC2 Therapeutics  
Protocol Number: MC2-01-C3

Page X of Y

Table 14.2.5 Summary of Calcium Metabolism  
HPA Population

MC2-01 Cream (N=XX)		
	Observed Value	Change from Baseline
Albumin-Corrected Serum Calcium (unit)		
Baseline		
N	XX	--
Mean (SD)	XX.X (XX.X)	--
Median	XX.X	--
Q1, Q3	XX, XX	--
Minimum, Maximum	XX, XX	--
Visit 3/Week 4		
N	XX	XX
Mean (SD)	XX.X (XX.X)	XX.X (XX.X)
Median	XX.X	XX.X
Q1, Q3	XX, XX	XX, XX
Minimum, Maximum	XX, XX	XX, XX
Visit 5/Week 8		
N	XX	XX
Mean (SD)	XX.X (XX.X)	XX.X (XX.X)
Median	XX.X	XX.X
Q1, Q3	XX, XX	XX, XX
Minimum, Maximum	XX, XX	XX, XX

<Continue for: 24 Hours Urinary Calcium Excretion (unit) and Ratio of Urinary Calcium to Creatinine>

MC2 Therapeutics  
Protocol Number: MC2-01-C3

Page X of Y

Table 14.2.6: Summary of Physician's Global Assessment (PGA)  
Safety Population

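### The HPA tables have no row for suppression at either visit, and the overall Week 8 row includes subjects whose cream was stopped at Week 4, so it cannot be read as the 8-week risk

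*Protocol*

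**What the plan says.** Protocol 4.2 defines the secondary HPA endpoint, for the cream arm only, as the number of subjects with a serum cortisol of 18 µg/dL "or less at 30 minutes after ACTH challenge at Week 4 or Week 8". The planned summary in Protocol 8.8.1 uses *and*: "The number and proportion of subjects with HPA-axis suppression at Week 4 and Week 8 will be" summarised. The synopsis also says *and*. Protocol 8.3 gives the purpose of the HPA analysis, which is to "estimate the risk to subjects with normal HPA function of HPA-axis suppression following treatment".

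Protocol 7.9.2 sets out what follows a positive Week 4 test: "If HPA axis is suppressed at Week 4, the subject should be contacted and the application with the MC2-01 cream should be discontinued". It then adds: "The subject should continue in the trial and the ACTH challenge test is repeated at the Week 8 visit".

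SAP 10.8.2.1 acknowledges the stop and continues: "Subjects with HPA-axis suppression at Week 8 will be summarised overall and separately by HPA-axis suppression status at Week 4". Tables 14.2.4.1 (cut-off below 18 µg/dL) and 14.2.4.2 (below 14 µg/dL) each have four rows: Week 4, Week 8, and Week 8 for those suppressed and those not suppressed at Week 4. The programming note under each table gives both split rows the same denominator, the subjects suppressed at Week 8.

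For calcium, SAP 10.8.2.2 says: "Observed values and changes from baseline to Week 4 and Week 8 will be summarized using descriptive statistics".

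**The concern.** The secondary objective is the effect of the cream on the HPA axis under maximum use, and the cream is meant for up to 8 weeks. A reader of the tables will want to know what share of subjects with a normal axis at baseline became suppressed at some point in those 8 weeks, and what share of those who kept applying the cream were suppressed at Week 8. No planned percentage answers either question.

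The overall Week 8 row looks like the answer to the first. However, it includes subjects tested about 4 weeks after their cream was stopped because of suppression (Day 28 to Day 56, less the time needed to get the result and contact the subject). Protocol 7.13.6 describes corticosteroid-induced suppression as usually reversible, so some recovery is plausible. Each recovered subject lowers the Week 8 figure, and suppression can then appear to fall with longer use because the affected subjects were taken off treatment.

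**Working it through.** **Inputs.** The plan gives no expected suppression rate and no statistical basis for the sample size (Protocol 8.2), so there is no stated figure to reproduce. The synopsis plans about 60 subjects at 1:1, hence about 30 on cream, and aims for 25 per arm in the PK population. The number evaluable for HPA is not stated; N = 25 and N = 30 are used as a range. All event counts below are assumptions.

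**Notation.** N subjects are tested at both visits. Of these, a are suppressed at Week 4, r of those a have recovered by Week 8, and b are newly suppressed at Week 8.

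- Week 4 row = a/N
- Overall Week 8 row = (a − r + b)/N
- Suppressed at either visit = (a + b)/N
- Either visit minus overall Week 8 = r/N

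The gap is never negative. One recovered subject is worth 1/25 = 4.0 points or 1/30 = 3.3 points.

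| N | a, r, b | Week 4 row | Overall Week 8 row | Either visit | Gap (points) |
|---|---|---|---|---|---|
| 25 | 1, 0, 0 | 4.0% | 4.0% | 4.0% | 0 |
| 25 | 1, 1, 0 | 4.0% | 0% | 4.0% | 4.0 |
| 25 | 3, 2, 1 | 12.0% | 8.0% | 16.0% | 8.0 |
| 25 | 5, 5, 0 | 20.0% | 0% | 20.0% | 20.0 |
| 30 | 1, 1, 0 | 3.3% | 0% | 3.3% | 3.3 |
| 30 | 3, 2, 1 | 10.0% | 6.7% | 13.3% | 6.7 |
| 30 | 5, 5, 0 | 16.7% | 0% | 16.7% | 16.7 |

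For the case 3, 2, 1 at N = 25, the exact 95% intervals are 1.0% to 26.0% for the Week 8 row (2/25) and 4.5% to 36.1% for either visit (4/25).

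**Do the split rows repair this?** Under the programming note they are (a − r)/(a − r + b) and b/(a − r + b). In the same case they print 1/2 and 1/2. These are shares of the Week 8 cases. The risks by Week 4 status would be (a − r)/a = 1/3 and b/(N − a) = 1/22. If every Week 4 case recovers and there are no new cases, both split rows are 0/0.

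**Does the row "HPA-Axis Not Suppressed at Week 4" isolate subjects still on cream?** It does not, for two reasons.

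- The stop follows the three-part definition in Protocol 7.9.2: basal cortisol at or below 5, 30-minute cortisol at or below 18, or an increment below 7 µg/dL. The SAP classifies on 30-minute cortisol alone. A subject stopped on basal level, on increment, or at exactly 18 counts as not suppressed at Week 4 in Table 14.2.4.1. In Table 14.2.4.2 the same applies to anyone stopped with a 30-minute value from 14 to 18.
- Protocol 6.4 allows clear subjects to stop after Week 4 and to restart.

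By contrast, the PK population requires the planned application at the visit concerned. The HPA population has no such condition.

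**Missing visits.** A subject suppressed at Week 4 with no Week 8 test has missing Week 8 status (SAP 10.8.1) and, without imputation (SAP section 7), cannot be a Week 8 case. A subject with no Week 4 test has no Week 4 status for the split. The early termination procedures in Protocol 7.16 list no ACTH test, so missing Week 8 results are possible.

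**The case against.** The strongest defence is that the SAP saw the problem. It mentions the stop at Week 4 and, in the next sentence, splits Week 8 by Week 4 status. With no missing visit, the either-visit count is the Week 4 numerator plus the Week 8 numerator among those not suppressed at Week 4, here 3 + 1 = 4. All results are also listed by subject. This stands: the information is not lost. What is missing is a printed count with a defined denominator, and the hand sum fails once a visit is missing.

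A reader might infer that the SAP has dropped a cumulative endpoint fixed in the protocol. The documents do not establish that. The next item in Protocol 4.2 uses the same *or* for calcium changes, where it can only mean each visit, and the synopsis and 8.8.1 say *and*. The wording is inconsistent, and the visit-wise rows fit one fair reading of it.

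A reader might also infer that the suppression risk will be understated. No passage calls the overall Week 8 row the 8-week risk. As a statement of status at Week 8 it is correct, and the Week 4 cases have their own row. The shortfall arises only if the row is read as cumulative risk, and only if someone recovers. Protocol 2.2 describes such effects with marketed combinations as infrequent.

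Finally, the calcium summaries might seem to be affected in the same way. They are not. A raised Week 4 calcium leads to a repeat test at Week 6 (Protocol 7.9.1), not to a stop. Subjects off cream for other reasons may dilute the Week 8 calcium change, but the calcium result does not select them.

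**Conclusion.** The point holds as a gap in the planned tables. Neither table prints suppression at either visit, and neither prints Week 8 suppression among subjects still applying the cream, although Protocol 8.3 and SAP section 8 aim at the risk following treatment. Taken as the risk over 8 weeks, the overall Week 8 row can err only downward when all subjects have both tests. The error is r/N: zero if no Week 4 case recovers, otherwise 4.0 points per recovered subject at N = 25 and 3.3 at N = 30. How many will recover cannot be judged from the documents, so the counts in the table show scale and are not a forecast. The split by Week 4 status is a sound idea, but its denominators and the two different suppression definitions prevent it from filling the gap.

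**What to change.** 1. Reconcile *Week 4 or Week 8* in Protocol 4.2 with *Week 4 and Week 8* in the synopsis and 8.8.1, so that it is clear whether an either-visit count is the endpoint.
2. Add to both tables a row *Suppressed at Week 4 and/or Week 8*. The denominator is the table's own analysis population with at least one post-baseline ACTH result. It should not depend on outcome, as it would if Week 4 cases without a Week 8 test were kept and non-cases without one were dropped.
3. Beside that row, state how many subjects were not suppressed at Week 4 and have no Week 8 result. As a sensitivity figure, give the proportion excluding everyone without both tests. For example, assume 30 subjects, 3 Week 4 cases all retested, 2 new cases at Week 8, and 5 non-cases without a Week 8 test. The main row is then 5/30 = 16.7% and the sensitivity figure 5/25 = 20%.
4. Label the overall Week 8 row *regardless of cream use after Week 4*.
5. Add a Week 8 row for subjects with no recorded stop of cream between Week 4 and Week 8, taken from the dosing and approved-stop records (Listings 16.2.5.1 and 16.2.5.4.1), with those tested at Week 8 as denominator. Define it by actual cream use and not by Week 4 cortisol class. It describes subjects who continued and does not replace the either-visit row.
6. For Table 14.2.5, an on-cream Week 8 summary is optional.

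The cost is SAP and table-shell wording plus the clarification in Protocol 4.2. No new data and no change to any clinical rule are needed. The reported suppression figure may be less favourable.

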##### Calcium metabolism evaluation for subjects assigned to the MC2-01 cream:

Changes from Baseline to Week 4 or Week 8 in:

- Albumin-corrected serum calcium;
- 24-hour urinary calcium excretion;
- Ratio of urinary calcium to creatinine.

#### **Safety Endpoints**

Safety endpoints include the following:

- Local skin reaction;
- Adverse events (AEs) and serious adverse events (SAEs);
- Changes in safety laboratory test results;
- Changes in ECGs (Only for subjects assigned to the MC2-01 cream);
- Changes in vital signs and physical examinations.

#### **Other Endpoints**

- For all subjects:  
The proportion of subjects with treatment success, defined as a minimum 2-point decrease from Baseline in the physician's global assessment (PGA) on the scalp, trunk, and limbs at Week 4.

- For subjects assigned to the MC2-01 cream:  
The proportion of subjects with treatment success, defined as a minimum 2-point decrease from Baseline in the PGA on the trunk, limbs, and scalp at Week 8.
- For all subjects:  
Subject assessment of treatment convenience at Week 4 using a Psoriasis Treatment Convenience Scale.

## 5.0 SELECTION OF TRIAL POPULATION

### 5.1 Subject Population

A sufficient number of subjects will be enrolled in order to provide 25 subjects in each treatment arm, who are included in the PK analysis at Week 4. An individual subject will be allowed to participate in the trial one time only. A rationale for the choice of sample size is provided in [Section 8.2](#) of this protocol.

Each potential subject will sign and date an informed consent document (ICF) before any trial-specified procedures are performed. Subjects will provide authorisation for use of their personal data in accordance with the applicable regulations regarding privacy and data protection.

### 5.2 Inclusion Criteria

Subjects must meet all the following criteria to be eligible for participation in the trial:

1. Have provided written informed consent.
2. Generally healthy males or non-pregnant females, of any race or ethnicity, who are at least 18 years of age at the time of screening.
3. At Visit 1/Day 0, have a clinical diagnosis of plaque psoriasis (psoriasis vulgaris) of at least 6 months duration involving trunk, limbs and/or scalp that is amenable to topical treatment with a maximum of 100 g of trial medication per week.
4. Have a PGA of severity of at least moderate on the trunk, limbs and/or scalp, excluding psoriatic lesions on the face, genitals, and intertriginous areas, at Visit 1/Day 0.
5. Have a treatment area between 20% and 30% of the BSA on the trunk, limbs and/or scalp, excluding psoriatic lesions on the face, genitals, and intertriginous areas, at Visit 1/Day 0.
6. Female subjects must be of either:
  - Non-childbearing potential, i.e., post-menopausal for a least 1 year or have a clinical history of sterility (e.g., hysterectomy or tubal ligation) or,
  - Childbearing potential with a negative urine pregnancy test prior to initiation of trial treatment, to rule out pregnancy.

7. Female subjects of childbearing potential must be willing to use effective contraception at trial entry and until completion. Effective contraception is defined as follows:
  - Oral/implant/injectable/transdermal/estrogenic vaginal ring contraceptives, intrauterine device, condom with spermicide, diaphragm with spermicide.
  - Abstinence or partner's vasectomy are acceptable if the female agrees to implement one of the other acceptable methods of birth control if these conditions do not any longer apply.

### 5.3 Exclusion Criteria

Subjects who fulfil any of the following criteria will be ineligible to participate in the trial:

1. Have a current diagnosis of unstable forms of psoriasis, including erythrodermic or pustular psoriasis.
2. Other inflammatory skin disease in the treatment area that may confound the evaluation of the psoriasis vulgaris (e.g., atopic dermatitis, contact dermatitis, tinea corporis);
3. Presence of pigmentation, extensive scarring, pigmented lesions or sunburn in the treatment areas, which could interfere with the rating of efficacy parameters;
4. Planned excessive or prolonged exposure to either natural or artificial sunlight, including tanning booths, sun lamps, etc.
5. Use of phototherapy (psoralen + ultraviolet A radiation [PUVA] and ultraviolet B radiation [UVB]) within 4 weeks prior to Visit 1/Baseline and during the trial;
6. Current or past history of disorders of calcium metabolism associated with hypercalcemia, vitamin D toxicity, severe renal insufficiency, or severe hepatic disorders;
7. Oral calcium supplements, vitamin D supplements, bisphosphonates or calcitonin within 4 weeks prior to Visit 1/Day 0 during the trial period.  
Note: Stable doses of oral vitamin D supplementation  $\leq 400$  IU/day are permitted provided there are no dose adjustments during the trial period;
8. Planned initiation of, or changes to concomitant medication that could affect calcium metabolism (e.g., antacids, thiazide and/or loop diuretics, antiepileptics) during the trial;
9. Planned initiation of, or changes to, concomitant estrogen therapy during the trial;
10. Strong systemic cytochrome P450 3A4 (CYP 3A4) inhibitors (e.g., clarithromycin, telithromycin, nefazodone, itraconazole, ketoconazole, atazanavir, darunavir, indinavir, lopinavir, nelfinavir, ritonavir, saquinavir, tipranavir) within 4 weeks prior to Visit 1/Day 0 and during the trial period;
11. Use of topical treatments (eg, corticosteroids, vitamin D analogs, retinoids, PDE4 inhibitors, salicylic acid, pimecrolimus, tacrolimus, anthralin, tar), except for emollients

and non-medicated shampoos, with a possible effect on psoriasis within 2 weeks prior to Visit 1/Day 0 and during the trial period;

12. Systemic treatment with biological therapies (whether marketed or not marketed), with a possible effect on psoriasis vulgaris within the following time period prior to Visit 1/Day 0 and during the trial period;
  - etanercept – within 4 weeks
  - adalimumab, alefacept, infliximab – within 8 weeks
  - ustekinumab – within 16 weeks
  - other products – within 4 weeks/5 half-lives (whichever is longer)
13. Initiation of, or expected changes to, concomitant medication that may affect psoriasis (e.g., beta-blockers, chloroquines, lithium, and angiotensin converting enzyme [ACE] inhibitors) and during the trial period;
14. Any of the following conditions, whether known or suspected:
  - depression and endocrine disorders (e.g. Cushing's disease, Addison's disease, diabetes mellitus) known to affect cortisol levels or HPA axis integrity
  - Non-nocturnal sleep patterns (e.g. night shift workers);
15. Use of systemic medication that suppresses the immune system (e.g, methotrexate, retinoids, PDE4 inhibitors, corticosteroids (excluding inhaled, nasal, auricular or ocular corticosteroids), ciclosporin [cyclosporine], and other systemic chemotherapeutic antineoplastic therapy) within 4 weeks prior to the Visit 1/Day 0 and during the trial period;
16. Have clinical signs of skin infection with bacteria, viruses, or fungi;
17. Known human immunodeficiency virus (HIV) infection;
18. Known or suspected of hypersensitivity to any component of the test product or reference product;
19. Have any chronic or acute medical condition that, in the option of the investigator, may pose a risk to the safety of the subject, or may interfere with the assessment of safety or efficacy in this trial;
20. Require the use of any concomitant medication that, in the investigator's opinion, has the potential to cause an adverse effect when given with the investigational product or will interfere with the interpretation of the trial results;
21. Females who are pregnant, breast feeding, or planning a pregnancy;

22. Participation in another clinical trial or received an investigational product or non-marketed drug substances within 30 days;
23. Previously enrolled in this trial;
24. In the opinion of the (sub)investigator, the subject is unlikely to comply with the clinical trial protocol;

